Comparative research assessing the efficacy of these breathing methods in elderly individuals immobilized after femur neck fractures is, however, lacking. Furthermore, only a few studies have used objective measurement instruments like volume-oriented incentive spirometry to look at their combined effects on blood pressure and inspiratory capacity. By methodically contrasting Box Breathing with Liuzijue Qigong, this randomized controlled experiment seeks to close this evidence gap and advance evidence-based cardiopulmonary rehabilitation techniques for this susceptible group.

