3.1 Research Design Outline

The study aims to perform a Comparative study on older people who have been immobilized due to femur neck fractures.in Saveetha Medical College and Hospital.

Formerly titled “Effectiveness of Liuzijue and Box Breathing Techniques on Inspiratory Capacity and Blood Pressure Following Femoral Neck Fracture Immobilization: A Retrospective Comparative Study” involves elderly with femoral neck fracture immobilization by Inspiratory capacity and blood pressure were assessed using a volumetric incentive spirometer and a digital sphygmomanometer, respectively. Improvement in inspiratory capacity was defined as an increase in measured values, with ranges progressing from approximately 1300 mL to 3000 mL. Improvement in cardiovascular status was considered when blood pressure remained within a stable range, with systolic values between 120-150 mmHg and diastolic values between 70-90 mmHg.

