4.1 Primary Outcomes

Statistical analysis will be performed using appropriate statistical software. Descriptive statistics, including mean and standard deviation, will be calculated for the primary outcome variables: Inspiratory capacity (mL) for both intervention groups.

To evaluate changes over time and differences between groups, a mixed-design repeated measures analysis of variance (ANOVA) will be used, with time (baseline, 2nd week, and 4th week) as the within-subject factor and group (Liuzijue Qi Gong exercise and Box Breathing technique) as the between-subject factor. This analysis will determine the effectiveness of the interventions across the different time intervals.

Post-hoc pairwise comparisons with Bonferroni correction will be conducted when significant main effects or interactions are observed. Mauchly's test of sphericity will be applied, and if the assumption of sphericity is violated ($p < 0.05$), the Greenhouse-Geisser correction will be used. A p -value < 0.05 will be considered statistically significant.

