4.2 Secondary Outcomes

Secondary outcome analysis will include systolic and diastolic blood pressure parameters to assess cardiovascular responses to the interventions. Descriptive statistics (mean \pm standard deviation) will be computed for each time point within and between groups.

A repeated measures ANOVA will be performed to examine within-group changes across time and between-group differences in blood pressure values. Where significant effects are identified, post-hoc analysis with Bonferroni adjustment will be carried out to explore pairwise differences between baseline, 2nd week, and 4th week measurements. In cases of sphericity violation, the Greenhouse-Geisser correction will be applied. Statistical significance will be set at $p < 0.05$.

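### A record review that is once called randomised compares two techniques without any adjustment, and the result is to be read as effectiveness

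*Combined protocol and SAP*

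**What the plan says.** **Design.** Section 2.1 says that "this randomized controlled experiment seeks to close this evidence gap". Sections 3.2 and 3.3 describe something else: patients were found through medical and physiotherapy records, had already received one technique or the other during rehabilitation, and were not enrolled prospectively. Sections 4.4 and 4.4.1 agree, describing existing records and a secondary analysis. Section 3.1 also contains "Femoral Neck Fracture Immobilization: A Retrospective Comparative Study", but as part of a title marked as a former one, so little weight is placed on it here.

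**Choice of technique.** No section says who chose the technique, on what grounds, or in which period.

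**Primary analysis (4.1).** A mixed ANOVA with time (baseline, week 2, week 4) as the within-subject factor and "group (Liuzijue Qi Gong exercise and Box Breathing technique) as the between-subject factor". Bonferroni pairwise comparisons "will be conducted when significant main effects or interactions are observed". The stated inference is "This analysis will determine the effectiveness of the interventions across the different time intervals".

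**Secondary analysis (4.2).** A repeated measures ANOVA of blood pressure "to examine within-group changes across time and between-group differences in blood pressure values", with follow-up tests "to explore pairwise differences between baseline, 2nd week, and 4th week measurements". Means and SDs "will be computed for each time point within and between groups".

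**Data.** Section 3.3 names only inspiratory capacity and blood pressure as extracted. It restricts the sample to patients who completed four weeks and have documented outcomes. Section 4 provides for percentages for categorical data. No covariate, matching, weighting or table of patient characteristics by group is specified.

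**The concern.** When treatment is not allocated at random, the groups may differ in how well they would have recovered anyway. Section 2.1 itself notes that comorbidity and delayed surgery are common in these patients and worsen pulmonary and haemodynamic status. Such factors may also influence which technique a patient is given. A model with only group and time attributes any resulting difference in recovery to the technique.

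Two features of the text make this worse. The effectiveness sentence draws a causal conclusion, and a reader who takes the design label in section 2.1 at face value would believe that randomisation supports it. In addition, the plan does not say which term of the ANOVA decides between the techniques. It therefore does not exclude reading a group main effect, which averages in the baseline visit, as a difference between them.

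**Working it through.** **1. The text.** There is no sample size, SD, power or effect size in the documents, so no figure of the plan's own can be reproduced. The check is mainly one of reading.

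| Question | What the document gives |
|---|---|
| Randomised? | Section 2.1 only. The other use of the word in the body text, in 2.2, describes a cited trial. |
| Record review? | 3.2, 3.3, 4.4, 4.4.1 |
| Reason for receiving a technique? | None given |
| Terms in the model? | Group and time (4.1); no covariate in 4.2 |
| Any control of confounding in section 4? | None |
| Inference? | Effectiveness (4.1) |

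**2. What the model can and cannot remove.** Baseline is a level of time, so a constant difference between groups cancels from the group-by-time interaction. A difference in expected change does not cancel. Nor does regression to the mean when the groups start at different levels.

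**3. Illustration.** All inputs are assumptions: n = 30 or 50 per group, equal outcome SD of 1 at each visit, equal between-visit correlation ρ of 0.5 or 0.7, no true difference between techniques, two-sided 5% tests. Shifts d are in SDs of the outcome.

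(a) *Stable difference of 0.3 SD, group main effect.* The SD of a patient's three-visit mean is √((1+2ρ)/3), which is 0.816 at ρ = 0.5 and 0.894 at ρ = 0.7. The noncentrality is 0.3 / (SD × √(2/n)). For n = 30, ρ = 0.5 this is 0.3 / (0.816 × 0.258) = 1.42, on 58 df.

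(b) *Recovery difference of 0, d/2, d at the three visits, interaction F.* λ = n·d² / (4(1−ρ)), df 2 and 4n−4. For n = 30, ρ = 0.5, d = 0.3: λ = 30 × 0.09 / 2 = 1.35, on 2 and 116 df.

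(c) *Same shift, unadjusted change from baseline to week 4, t-test.* The SD of change is √(2(1−ρ)), and the noncentrality is d / (SD × √(2/n)). For n = 30, ρ = 0.5, d = 0.3 this is 0.3 / (1 × 0.258) = 1.16.

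Probability of p < 0.05 (exact noncentral t and F), shown as ρ = 0.5 / ρ = 0.7:

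| Test and shift | n = 30 per group | n = 50 per group |
|---|---|---|
| (a) Main effect, stable 0.3 | 28.8% / 24.8% | 44.4% / 38.2% |
| (b) Interaction, d = 0.1 | 6.1% / 6.9% | 6.9% / 8.2% |
| (b) Interaction, d = 0.2 | 9.7% / 13.0% | 13.1% / 19.2% |
| (b) Interaction, d = 0.3 | 16.1% / 24.4% | 24.6% / 38.7% |
| (c) Week-4 change, d = 0.1 | 6.7% / 7.8% | 7.9% / 9.8% |
| (c) Week-4 change, d = 0.2 | 11.9% / 16.6% | 16.8% / 24.8% |
| (c) Week-4 change, d = 0.3 | 20.8% / 31.4% | 31.8% / 48.3% |

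Simulation of 20,000 studies per setting, with the planned Mauchly and Greenhouse-Geisser steps, gave 4.9% to 5.0% for the interaction under the stable shift. Its other results were within 1 percentage point of the exact values.

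**4. Reading the table.** The interaction holds its level against a stable difference and loses it against a difference in recovery. At a fixed shift the rates rise with more records. Row (c) shows that naming a week-4 contrast without adjusting it does not solve the problem. Bonferroni and Greenhouse-Geisser corrections address other matters.

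**The case against.** The strongest objections are these.

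- **Baseline is already in the model.** This is correct, and it protects the interaction against a stable difference. It does not protect against differing recovery, and the interaction is not named as the deciding test.
- **The main-effect reading is speculative.** In part it is. The follow-up tests in 4.2 are between visits, and a two-group main effect needs no further pairwise test. The text only fails to exclude that reading. The 25% to 44% in row (a) apply only if it is adopted.
- **No imbalance is shown, and every input is assumed.** This stands. At a 0.1 SD recovery shift the rates are 6.1% to 8.2% for the interaction and 6.7% to 9.8% for the week-4 contrast, not far above nominal. Confounding could also hide a true difference. The finding rests on the text, not on these percentages.
- **The effectiveness sentence may mean change over time within each group.** On that reading, natural recovery and repeated practice with the spirometer are the rival explanations, and there is no untreated group to separate them. Adjustment would not help, but wording the result as association covers this reading too.
- **Other fields were evidently read.** Section 3.2 refers to eligibility criteria documented in the records, and the list in 3.3 is not stated to be complete. This makes adjustment more feasible. It does not put adjustment into the plan.

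**Conclusion.** The concern holds, with high confidence, and should be corrected before outcomes are analysed. One sentence labels the study randomised against four sections that describe a record review. The comparison of techniques has no control of confounding, and its result is to be called effectiveness. If the groups differed in expected recovery, the planned test could not separate that from an effect of technique.

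Whether they differ, and by how much, is unknown. Under the stated assumptions, a recovery difference of 0.2 to 0.3 SD by week 4 raises the false-positive rate of the interaction from 5% to 10%–24% at 30 per group and 13%–39% at 50.

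**What to change.** 1. **Reconcile the label.** Bring section 2.1 into line with 3.2, 3.3, 4.4 and 4.4.1. If the sponsor confirms the record review, call it a retrospective non-randomised comparison. State how technique was chosen, or that this is unknown. Replace the effectiveness sentence in 4.1 with wording about association. If any patients had in fact been randomised, document the allocation instead.
2. **Name the contrast.** In 4.1 and 4.2, state that techniques are compared by the group difference in change from baseline at one visit fixed in advance (for example week 4), not by the group main effect.
3. **Adjust and tabulate.** Report that contrast with a 95% CI, adjusted for a short pre-specified set of recorded pre-treatment covariates and their interactions with time. Candidates are age, sex, operated or not, days immobilised before baseline, respiratory comorbidity and cardiovascular comorbidity, plus antihypertensive use for blood pressure. Before outcomes are analysed, cap the set by the sample size, keep only fields recorded in nearly all patients, and state how a missing covariate is handled. Tabulate the covariates, and how often each is recorded, by group.
4. **State what remains.** Unmeasured confounding and the restriction to completers in 3.3 are not removed by adjustment. A sensitivity analysis adjusted for the baseline value is optional.

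**Cost.** SAP wording and some further extraction. The availability of the fields must be checked first, as must the fit with the consent waiver in 4.4 and the de-identification in 4.4.2. At an assumed 60 patients, the change contrast goes from 60 − 2 = 58 df to 60 − 2 − 6 = 52 for inspiratory capacity and 60 − 2 − 7 = 51 for blood pressure. If each field were missing independently in 2% to 5% of records (assumed), a complete-case analysis would keep 60 × 0.98⁶ ≈ 53 to 60 × 0.95⁶ ≈ 44 patients with six covariates. With seven it would keep 60 × 0.98⁷ ≈ 52 to 60 × 0.95⁷ ≈ 42. The claim also becomes more modest.

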3.2 Participants

This retrospective study included elderly individuals diagnosed with femoral neck fracture who had undergone a period of immobilization and subsequently received either Liuzijue Qi Gong exercise or Box Breathing technique as part of their rehabilitation program. Participants were identified through a review of medical and physiotherapy records from Saveetha Medical College and Hospital. Eligibility was determined based on inclusion and exclusion criteria documented in the clinical records.

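### Section 4.1 attaches an effectiveness conclusion to a mixed ANOVA that cannot show it with two active arms, and does not name the term that decides between the techniques

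*Combined protocol and SAP*

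**What the plan says.** For inspiratory capacity, section 4.1 states: "To evaluate changes over time and differences between groups, a mixed-design repeated measures analysis of variance (ANOVA) will be used". Patients are compared between the two techniques and within themselves over three visits, and baseline counts as one of those visits. The section then attaches the conclusion: "This analysis will determine the effectiveness of the interventions across the different time intervals". It also provides Bonferroni-corrected pairwise follow-up whenever a main effect or an interaction is significant. No term, visit or contrast is named as the deciding one.

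For systolic and diastolic pressure, section 4.2 says: "A repeated measures ANOVA will be performed to examine within-group changes across time and between-group differences in blood pressure values". The follow-up comparisons it spells out are between the three visits.

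Three other places bear on the point:

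- Sections 3.2 and 3.4 show that every included patient received one of the two techniques. There is no untreated or usual-care group.
- Section 3.1 defines improvement in inspiratory capacity as a rise in the measured value, which is a pre-post criterion.
- On allocation, section 2.1 says "By methodically contrasting Box Breathing with Liuzijue Qigong, this randomized controlled experiment seeks to close this evidence gap". The former title in section 3.1 ends "A Retrospective Comparative Study", and section 3.2 says "This retrospective study included elderly individuals diagnosed with femoral neck fracture". Sections 3.3, 4.4 and 4.4.1 also describe a review of existing records.

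**The concern.** The model yields three tests: group, time and group-by-time. They answer different questions, and section 4.1 gives all three one conclusion. Its stated purposes, and those of section 4.2, are most easily read as the two main effects, and neither answers the comparative question.

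Two unsupported conclusions are therefore left open. One technique could be called better because of a gap that existed before treatment. Both could be called effective because patients changed over four weeks, with nothing to show what would have happened without the exercises. The pre-post definition of improvement in section 3.1 makes the second reading a natural one.

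**Working it through.** The plan gives no sample size, effect size or power, so there is no figure of its own to reproduce. The check has an algebraic part, which needs no assumptions about n, SD or correlation, and an illustration, which does.

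**Algebra.** Let d0, d2 and d4 be the true group differences at baseline, week 2 and week 4. Baseline is a level of time, so the group main effect is (d0 + d2 + d4)/3.

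- Persistent pre-treatment gap b, no treatment difference: (b + b + b)/3 = b. The gap enters in full.
- Balanced baseline, difference d reached linearly at week 4: (0 + d/2 + d)/3 = d/2.
- Balanced baseline, difference d at both post visits: (0 + d + d)/3 = 2d/3.
- With any balanced baseline, (d2 + d4)/3 is two thirds of the average post-baseline difference.

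The time main effect averages over two treated groups, so treatment, recovery and any other common change are inseparable in it. Group-by-time removes a constant baseline gap, but it supports only a statement about one technique relative to the other.

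**Illustration: assumptions.** Unit variance, equal correlation r between visits, n = 30 per group, two-sided alpha 0.05, r = 0.3/0.5/0.7. None of these except the 0.05 is in the documents.

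- Group: F(1, 2n−2), λ = (n/2)·d̄² / ((1+2r)/3)
- Group-by-time: F(2, 2(2n−2)), λ = (n/2)·Σ(d−d̄)² / (1−r)
- Time: F(2, 2(2n−2)), λ = 2n·Σ(m−m̄)² / (1−r), where m are the visit means
- Week-4 change contrast: noncentral t, df 2n−2, nc = (d4−d0)/√(2(1−r)·2/n)
- Baseline-adjusted week 4: noncentral t, df 2n−3, nc = (d4−r·d0)/√((1−r²)(2/n + d0²/(2n−2)))

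**Worked case, r = 0.5.**

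- Constant gap of 0.3. Group: λ = 15 × 0.09/(2/3) = 2.025 on F(1, 58), rejecting in 28.8%. Group-by-time: Σ(d−d̄)² = 0, so 5%.
- Common change 0, 0.15, 0.30 in both groups. Time: Σ(m−m̄)² = 0.045, λ = 60 × 0.045/0.5 = 5.4 on F(2, 116), rejecting in 52.6%.
- Difference 0, 0.25, 0.5. Group: λ = 15 × 0.0625/(2/3) = 1.41. Group-by-time: λ = 15 × 0.125/0.5 = 3.75. Change: nc = 0.5/√(1/15) = 1.94. Adjusted: nc = 0.5/√0.05 = 2.24.

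**Percent significant, 30 per group, r = 0.3/0.5/0.7.**

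| Group differences (baseline, week 2, week 4), SD | Group | Group-by-time | Week-4 change | Baseline-adjusted week 4 |
|---|---|---|---|---|
| Constant gap: 0.3, 0.3, 0.3 | 34.7/28.8/24.8 | 5.0 | 5.0 | 13.2/10.0/7.6 |
| Regressing gap: 0.3, 0.3r, 0.3r | 13.3/15.4/17.6 | 9.9/8.5/7.0 | 10.4/8.8/7.3 | 5.0 |
| Linear real difference: 0, 0.25, 0.5 | 25.6/21.5/18.7 | 28.4/38.3/59.1 | 36.3/47.8/69.1 | 51.4/59.4/76.0 |
| Sustained: 0, 0.5, 0.5 | 41.2/34.3/29.5 | 36.7/49.3/72.4 | 36.3/47.8/69.1 | 51.4/59.4/76.0 |
| Fading: 0, 0.5, 0.25 | 25.6/21.5/18.7 | 28.4/38.3/59.1 | 12.7/15.9/23.3 | 17.0/19.6/26.6 |

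The first two rows have no treatment difference. The exact 5% for the adjusted test in the second row is built in, because the later gaps are set to r times the baseline gap.

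Time term with a common linear 0.3 SD change in both groups: 39.3/52.6/75.9%.

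**Other sample sizes.** At 20 per group the constant-gap group term is 24.5/20.5/17.9% and the time term 27.1/36.5/56.6%. At 50 per group they are 52.9/44.4/38.2% and 60.9/76.4/94.1%.

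**The case against.** The best reply is that section 4.1 already contains the right test. The planned model includes group-by-time, and the SAP says significant interactions will be followed up. Effectiveness across the time intervals can be read as that term. Section 4.2 also plans blood-pressure summaries by visit and group, so a baseline gap in blood pressure would be visible.

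Most of this stands. A reader might infer that the plan omits the interaction, or that it commits to reading the group main effect as a treatment effect. The documents support neither inference: the interaction is tested, and no sentence says how the group term will be interpreted. What the reply does not answer is that the choice among three tests is left until after the results, and that even the interaction cannot establish effectiveness without an untreated comparator.

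A reader might also infer that the group term always has less power. It does not. With a 0.5 SD difference at both post visits and r = 0.3, it has 41% against 36% for the week-4 change contrast. The dilution of the estimate relative to the average post-baseline difference is general when baseline is balanced; the power ranking depends on the trajectory.

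Nor are the first table row and the time-term figures error rates of faulty F tests. Those tests correctly detect real mean differences; the mistake would be in what those differences are taken to mean.

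Finally, random allocation would reduce a baseline gap to chance imbalance. The dilution and the missing untreated comparator would remain.

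**Conclusion.** The point holds and should be fixed. Section 4.1 promises a conclusion that no term in a two-active-arm design can give, and it leaves the comparative conclusion untied to a term. The mixed ANOVA itself is usable.

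The algebra is firm. The percentages are illustrations that depend on the assumed n, SD scale, correlation and trajectory. Over 20 to 50 per group and r from 0.3 to 0.7, a constant 0.3 SD gap with no treatment difference makes the group term significant in 18 to 53% of studies, and a common 0.3 SD change makes the time term significant in 27 to 94%.

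Whether a systematic baseline gap is likely depends on allocation. Sections 3.1 to 3.3, 4.4 and 4.4.1 point to non-random groups. The conflicting phrase in section 2.1 is a separate matter to reconcile.

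**What to change.** Amend 4.1, and 4.2 in parallel, before the outcome data are accessed. Section 3.3 describes data already recorded, so naming a contrast in advance has force only on that condition.

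1. Base the between-technique conclusion on group-by-time, or on one named contrast within it (for example the difference in change from baseline to week 4), with estimate and 95% CI.
2. Report the baseline-adjusted difference at the same visit alongside it. The two methods fail under opposite assumptions about a baseline gap, as the first two table rows show. If allocation proves to have been random, the adjusted difference can be the main analysis.
3. State that the group main effect including baseline is not read as a treatment difference and that within-group change over time is descriptive. Replace the effectiveness sentence with: *This analysis compares the two techniques.* State that the pre-post definition of improvement in section 3.1 is descriptive only.
4. If allocation was not random, state that the contrast remains open to confounding and regression to the mean.

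The cost is wording, a contrast inside the planned model and one simple added analysis; no new data are needed. There are two downsides. Effectiveness can no longer be claimed from pre-post change. A single week-4 contrast also loses power if the difference peaks at week 2: for 0.5 SD fading to 0.25 SD it has 13/16/23%, against 28/38/59% for the 2-df interaction. Designating the full interaction avoids that loss but gives no single estimate. The change does not remove confounding.

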3.3 Recruitment

For this retrospective analysis, medical and physiotherapy records of patients with femoral neck fracture immobilization treated at the Saveetha Medical College and Hospital were reviewed.

Records of participants who had completed a four-week intervention program and had documented outcome measures were included in the study. No direct recruitment or prospective enrollment was undertaken.

Data related to inspiratory capacity measured using a volumetric spirometer and blood pressure assessed using a digital sphygmomanometer were extracted from patient records. Outcome measures recorded at baseline (pre-intervention), at the second week and at the fourth week were included for analysis. Confidentiality of patient information was maintained and the study procedures were conducted under the approval and supervision of the institutional ethics committee and the principal investigator.

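### Single-step Bonferroni over the three visit pairs (Sections 4.1 and 4.2) is valid but needlessly conservative; a Holm step-down keeps the same 5% family-wise guarantee and never rejects less

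*Combined protocol and SAP*

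**What the plan says.** Section 4.1 plans a mixed repeated measures ANOVA of inspiratory capacity, comparing the two techniques, "with time (baseline, 2nd week, and 4th week) as the within-subject factor". It then adds: "Post-hoc pairwise comparisons with Bonferroni correction will be conducted when significant main effects or interactions are observed". The level is fixed by "A p -value < 0.05 will be considered statistically significant".

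Section 4.2 plans a repeated measures ANOVA for systolic and diastolic pressure. Where effects are significant, "post-hoc analysis with Bonferroni adjustment will be carried out to explore pairwise differences between baseline, 2nd week, and 4th week measurements".

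Neither section names a step-down procedure, states how many comparisons the Bonferroni factor covers, or says which F test opens which comparisons. Section 4.2 limits the pairs to visits; Section 4.1 does not.

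**The concern.** Three visits give three pairs: baseline to week 2, baseline to week 4, and week 2 to week 4. Single-step Bonferroni holds all three at 0.0167 whatever the others show. Yet the three equalities are linked: if two hold, so does the third. Once one pair truly differs, at most one equality can still be true, and protecting it at 0.0167 is more than a 5% family-wise limit asks.

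At stake is the plan's ability to say when a change occurred. The F test for time shows only that some visit differs. The post-hoc pairs are the planned tests that place the change before or after week 2. The loss falls mainly on these two-week steps, which are usually smaller than the full four-week change.

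**Working it through.** **Inputs from the documents.** Alpha is 0.05 (Section 4.1; taken as two-sided, since the side is not stated). There are three visits and two groups. Greenhouse-Geisser is used "if the assumption of sphericity is violated". There is no power figure to reproduce: Section 3.3 says only that "Records of participants who had completed a four-week intervention program and had documented outcome measures were included in the study", and no sample size, SD, correlation, target effect or power appears anywhere.

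**Step 1: thresholds.** With a family of three, 0.05/3 = 0.0167 per pair under Bonferroni. Holm orders the p-values and compares them with 0.05/3 = 0.0167, 0.05/2 = 0.025 and 0.05/1 = 0.05, stopping at the first failure. Each Holm threshold is at least 0.0167, so Holm rejects whatever Bonferroni rejects.

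**Step 2: cost of a stricter level for one pair.** By normal approximation, power = Φ(δ − z), with z = 1.960, 2.241 and 2.394 for two-sided 0.05, 0.025 and 0.0167.

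| Power at 0.05 | at 0.025 | at 0.0167 | Loss, 0.05 to 0.0167 |
|---|---|---|---|
| 80% | 71.2% | 65.8% | 14.2 points |
| 90% | 84.1% | 80.2% | 9.8 points |
| 58.6% | – | 41.4% | 17.2 points (the maximum) |

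Holm recovers the whole loss for a pair only when the other two are rejected, because only then is that pair tested at 0.05.

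**Step 3: a worked scenario (assumed).** SD 1; visit correlations 0.7 (baseline–week 2), 0.6 (baseline–week 4) and 0.7 (week 2–week 4); means 0, 0.3 and 0.6 SD; 40 patients.

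- Two-week step: SD of the difference = √(2(1 − 0.7)) = 0.775, so δ = 0.3 × √40 / 0.775 = 2.45. Approximate power at 0.0167 is Φ(2.45 − 2.394) ≈ 52%, and at 0.05 it is Φ(2.45 − 1.960) ≈ 69%.
- Simulation (40,000 datasets; time F test at 5% as the gate, Greenhouse-Geisser when Mauchly's test is significant, then paired t-tests): 49% under the plan and 62% under Holm for each two-week step. The plan's 49% is a little below the 52% approximation because t-tests are used.
- With 60 patients: 70% under the plan and about 82% under Holm.
- Baseline to week 4, the largest contrast: about 95% under either rule with 40 patients.

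**Step 4: range over other scenarios.** For total N of 20 to 60, correlations of 0.5 to 0.8 and various visit profiles, the gain per pair runs from 0 to about 17 points. It is largest when two pairs are clearly different and the third is moderate. The largest contrast gains about 2 points or less.

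**Step 5: error rates.**

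| Situation | Bonferroni after gate | Holm after gate |
|---|---|---|
| No visit differs (family-wise) | 3.4%–3.9% | 3.4%–3.9% |
| Week 2 = week 4, baseline differs (error on the one true null) | 1.5%–1.7% | 2.1%–5.1% |

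The 5.1% is simulation noise around Holm's 5% limit. Without the gate, Bonferroni's family-wise rate is 4.4%–4.7% when no visit differs. The gate itself costs at most about 2 points of power, and almost nothing when effects are clear.

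**The case against.** The strongest reply is that nothing here is wrong: the SAP prespecifies a standard adjustment that controls family-wise error, and choosing another is taste. The first half stands. The second does not, because Holm gives the same guarantee under any dependence, needs no added assumption, and never rejects less.

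Other points against the concern:

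- **The family of three is an assumption for Section 4.1.** This stands. With six comparisons the level would be 0.05/6 = 0.0083, and with nine 0.0056. Between-technique contrasts at each interval are not specified in either section, so advice about them is conditional.
- **Holm does not use the link between the three equalities.** True. That link would allow more than 0.025 at the second step. Holm is a modest change that relies on neither the link nor the gate. The gate could not carry the burden in Section 4.1: if any of three F tests can open it, the chance under the null is 1 − 0.95³ = 14.3% if they are independent.
- **The consequence is limited.** This stands too. The visit pairs describe change over time in retrospective records of programme completers, and Section 4.2 calls them exploratory. A true null pair also faces a higher error rate under Holm, though within 5%.

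A reader might infer three stronger things. One is that the post-hoc tests run at 1.7% family-wise instead of 5%. But 1.7% is a per-pair level, and it equals the family-wise rate only when exactly one pair is null. Another is that the 13-point gain in the worked scenario (49% to 62%) is a bound. It is one assumed case, and the documents supply none of its inputs. The third is that gating on the ANOVA causes the loss. Nearly all of it comes from the single-step correction.

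**Conclusion.** The point holds as an efficiency improvement, not as an error in the plan. Single-step Bonferroni over three visit pairs is valid but more conservative than the family-wise control the plan has chosen, and Holm is at least as powerful everywhere. The gain is 0 to about 17 points of power per pair, depending on sample size, correlation and the pattern of change, none of which the documents give. It goes mainly to the smaller contrasts. This assumes two-sided tests and a family of three. No conclusion about which technique is better changes through the group-by-time F test. Priority is low, but the change is cheap.

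**What to change.** In Sections 4.1 and 4.2, replace the Bonferroni correction with a Holm step-down adjustment over the three visit pairs, comparing the ordered unadjusted p-values with 0.0167, 0.025 and 0.05 and stopping at the first failure. Use one family per outcome. If between-technique contrasts at each interval are tested after a significant interaction, name those three as a separate Holm family.

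In the same edit, state the size of each family and which F test opens it. Holm is valid whether or not the gate is kept. Fix the rule before results are seen.

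Report adjusted p-values, with p1 the smallest: 3·p1; then the larger of that and 2·p2; then the larger of that and p3; each capped at 1.

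The cost is a sentence or two in each section and ordering three p-values by hand from the SPSS output. Holm has no simple matching simultaneous confidence intervals, so show ordinary 95% intervals beside the adjusted p-values and label them as unadjusted.
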